Subjects in whom the CD-related corticosteroids (systemic or rectal corticosteroids) that were not being taken at Baseline and are initiated during the study or who have equivalent dose of these medications increased to greater than the dose taken at Baseline will be censored for efficacy assessments (i.e., will be considered non-responders for categorical endpoints and will have Baseline values carried forward for non-categorical assessments) from that point through the end of the study. These subjects will continue to be evaluated in the safety population.

The equivalent steroid dose will be determined based on the table below:

| Corticosteroid | Equivalent Dose (mg) |
|--------------------|----------------------|
| Cortisone | 25 |
| Hydrocortisone | 20 |
| Prednisone | 5 |
| Prednisolone | 5 |
| Triamcinolone | 4.0 |
| Methylprednisolone | 4.0 |
| Betamethasone | 0.75 |
| Dexamethasone | 0.75 |
| Budesonide | 1 |
| Beclomethasone | 5 |
| Beclometasone | 5 |

Definition of Missing Data Imputation

The following imputation methods will be used to impute missing values in the efficacy analyses. In addition, an observed case analysis will be performed.

Non-Responder Imputation (NRI)

The NRI approach is used for binary efficacy variables. These variables can take values of 'Achieved' or 'Not Achieved' or may be missing for any reason including discontinuation from study. According to the NRI imputation approach, all missing values will be considered as 'Not Achieved.'

Last Observation Carried Forward (LOCF)

For all variables (categorical variables and continuous variables), the following rules will be used for the LOCF approach:

1. Baseline and Pre-Baseline values will not be used to impute the missing Post-Baseline values.

2. Missing values after Study Day 1 will be imputed using the latest non-missing values after Day 1 and prior to the missing value. If there are no non-missing values after Baseline, then the LOCF value will be missing.

Observed Case (OC)

Observed case analysis will be performed such that missing values will not be imputed.

However, all observed values will be replaced by Baseline value once subjects received CD-related corticosteroid therapy.

Mixed-Effect Model Repeated Measure (MMRM)

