The MMRM model will be used for continuous efficacy variables with longitudinal data as the primary analysis. The MMRM model includes the baseline values as covariate; randomization strata, treatment, time point and treatment-by-time point interaction as fixed effects; and subjects within treatment as random effect. An unstructured (co)variance structure will be used to model the within-subject error. The comparison at a time point will be the contrast between treatments at that time point. Satterthwaite's approximation will be used to estimate denominator degrees of freedom.

Imputation of Missing Dates

For Baseline, efficacy, and safety parameters, if the day and/or month are missing, the following conventions will be used to impute the missing dates:

- 01 for missing start day
- End of month for missing end day
- January 1st for missing start month
- December 31st for missing end month

In case of partially missing AE start and stop dates, the dates will be imputed by comparing to first dose date of study medication so that the corresponding AEs will be

made treatment-emergent whenever possible. If the start date of an AE is partially missing and the month is the same as the start date of a new therapy, the AE will be made treatment emergent to the new therapy.

In case of missing or partially missing study drug dosing dates, the dates will not be imputed. Subjects will be treated as not receiving dose on that date.

Rule for CDAI Calculation

Up to 14 days of diary entries will be evaluated from the ePRO tool for the CDAI calculation for each visit. The diary entries on the days the subjects receive endoscopy preparation medications, the day of endoscopy procedure, and 2 days after endoscopy procedure will be excluded. For each CDAI subscore, the available scores from the most recent diary days (at least 4 days, up to 7 days) prior to actual day of the study visit will be summed, and then multiplied by the corresponding multiplier to get subtotal score. If available diary entries are fewer than 7 days, the subtotal score will be calculated as (summed total available score/number of days) \times 7 \times corresponding multiplier. The three subtotal scores that are based on ePRO (number of liquid/very soft stools, abdominal pain rating, and general well-being) will then be rounded to one decimal. The final CDAI is rounded to a whole number.

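### Partial start dates for CD-related corticosteroids are imputed to the earliest date with no on-treatment safeguard, so some rescue use can be read as Baseline use and escape the steroid-failure rule

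*SAP*

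**What the plan says.** Both SAPs, in section 6.0 under Imputation of Missing Dates, give one general rule: "For Baseline, efficacy, and safety parameters, if the day and/or month are missing, the following conventions will be used to impute the missing dates". For start dates the conventions are "01 for missing start day" and "January 1st for missing start month".

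Two kinds of date are then treated differently:

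- Adverse events: "In case of partially missing AE start and stop dates, the dates will be imputed by comparing to" first dose, so that the event is treatment-emergent where the known parts of the date allow it.
- Dosing records: "In case of missing or partially missing study drug dosing dates, the dates will not be imputed".

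No exception is made for corticosteroids.

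Section 6.0 of the Induction SAP, under CD-Related Corticosteroid Use, has two triggers for steroid failure. One is a steroid "that were not being taken at Baseline and are initiated during the study". The other is an "equivalent dose of these medications increased to greater than the dose taken at Baseline". From that point such subjects "will be considered non-responders for categorical endpoints". The Extension SAP has an equivalent rule and judges new use against Induction Baseline. In both SAPs censoring lasts to the end of the study. Baseline is the last available value up to and including the day of first dose.

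**The concern.** A steroid that is really started after first dose, but recorded with a partial date, can be given an imputed start on or before first dose. On paper it is then Baseline medication, so the new-use trigger does not fire. The rescue dose can also become the Baseline dose against which later increases are judged. In the same way, a partially dated record of a dose increase can raise the apparent Baseline dose.

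Three things are at stake:

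- A subject who should be a non-responder stays eligible as a remitter on both co-primary endpoints and on the categorical secondary endpoints.
- The subject can enter analyses where he or she does not belong: the four steroid-free endpoints among Baseline users (Induction SAP 10.3), the Baseline corticosteroid subgroup (10.5) and the Baseline tables (7.1).
- A start missed during induction carries into the Extension analyses, because the failure status that should have lasted to the end of the study was never set.

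**Working it through.** The plan gives no figure for this, so there is nothing to reproduce. The check counts how often the date rules move a true post-Baseline start to on or before first dose.

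**Inputs**

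- Date rules, Baseline definition and steroid triggers: section 6.0 of both SAPs.
- Induction window: starts on Rx Day 2 to 113, which is 112 possible days (Week 16 is nominally Day 113 in the Induction SAP visit windows).
- Extension window: Day 114 to 365 counted from first induction dose, which is 252 possible days.
- 35 subjects per arm: Induction SAP 4.3 and Protocol 8.2.
- Assumption, not in the documents: first-dose dates are uniform over a 365-day year, and true steroid starts are uniform over the window.

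**1. Day missing, month known.** The 1st of the recorded month falls on or before first dose only if the steroid began in the calendar month of first dose. In a month of L days, the pairs of first-dose day and later start day number L(L − 1)/2. That is 465 for each of seven 31-day months, 435 for each of four 30-day months and 378 for February.

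- Affected pairs: 7 × 465 + 4 × 435 + 378 = 5,373
- All pairs: 365 × 112 = 40,880
- Share: 5,373 / 40,880 = **13.1%** (12.3% if the imputed date must be strictly before first dose)

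The share depends strongly on when the steroid really began:

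| True start | Moved to on or before first dose |
|---|---|
| Day 2–31 | 49% |
| Day 15–113 | 4.8% |
| Day 29–113 | 0.2% |
| Day 57–113 | 0% |

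In the other 87% or so, the imputed date is after first dose and no later than the true date, so the subject is still censored, on time or early.

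**2. Month missing, year known.** January 1st falls on or before first dose whenever the steroid began in the calendar year of first dose. Pairs that cross into the next year number 112 × 113 / 2 = 6,328.

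- Share: (40,880 − 6,328) / 40,880 = 34,552 / 40,880 = **84.5%**

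By month of first dose this is about 100% for January to August, 94% for September, 68% for October, 41% for November and 13% for December.

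**3. Steroids started in the extension.** The shortest gap from first induction dose is 113 days, so the calendar month cannot be shared.

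- Day missing: **0%**
- Month missing: (252 × 253 / 2) / (365 × 252) = 31,878 / 91,980 = **34.7%**

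**4. Mixture of partial dates (induction).** If a share w of partial dates lacks only the day, the overall share is 13.1% × w + 84.5% × (1 − w). This gives 20% at w = 0.9, 31% at w = 0.75 and 49% at w = 0.5.

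**5. Effect per subject.** One rescued subject wrongly kept as a remitter moves an arm by 1/35 = 2.9 points, and two move it by 2/35 = 5.7 points. The planning gap is 35% − 12% = 23 points.

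**The case against.** The strongest case against is that harm needs several things at once: a partial date, the calendar coincidence, no contradicting Baseline record, and remission despite rescue. The protocol works against the first and third. Section 5.2.3.1 requires start and end dates, Table 1 has concomitant medication reviewed at Baseline and at every study visit, section 11.0 plans logic checks for inconsistent dates, and section 8.1.10 has discrepancies resolved before lock. With induction visits two to four weeks apart, a missing month for a newly started steroid is the less plausible kind of gap, and that is the kind where the rule does most damage. For subjects who enter on steroids, section 5.2.3.2 allows no dose change in the first two weeks, so for a day-missing dose increase the relevant figure is nearer 4.8% than 13.1%. The SAPs also do not say that Baseline steroid status is derived from an imputed start date.

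Most of this stands, and it limits how often the problem can arise. It does not remove it. Both SAPs provide for partial dates, apply the rule to Baseline and efficacy parameters, and name no other source for steroid status.

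Two stronger readings are tempting and should not be drawn.

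- A reader might note that 353 of 365 calendar dates (96.7%) are not the 1st of a month, and infer that a missing day nearly always puts the start before Baseline. That figure matters only for a steroid begun in the month of first dose, which is about 13% of induction starts.
- A reader might infer that the error favours the drug, since it can only turn failures into possible successes. That is true within an arm but not between arms. If rescue is commoner on placebo, the comparator rate rises and the dose-response is diluted. In the steroid-free endpoints, a subject wrongly added to the denominator counts as a failure unless the steroid is stopped, which lowers the rate.

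**Conclusion.** The gap is real but minor. Followed as written, the date rule can turn true rescue into Baseline use, and the steroid-failure rule then does not apply. For induction starts this affects about 85% of month-missing dates and about 13% of day-missing dates. For extension starts the figures are about 35% and 0%. They rest on uniform first-dose and start dates, and on steroid status being taken from the imputed date when no other record settles it.

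The documents do not give the number of partially dated steroid records; it is probably small. Nor do they establish a direction for the bias in the comparison of arms. The case for acting is that the rule bears on the co-primary endpoints, the SAPs already protect adverse events against the same problem, and the change is cheap.

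**What to change.** Add one sentence to section 6.0 of each SAP. It should cover any CD-related corticosteroid start or dose-increase record that has a partial date and no documentation, from the Baseline medication record or the stop date, that it applied before first dose. For such a record, impute the earliest date after first induction dose that fits the known parts of the date, and treat the steroid as initiated or increased during the study. This mirrors the adverse-event rule. For true post-Baseline starts with no record of earlier use, the share moved to on or before first dose falls to 0%.

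The cost is one sentence per SAP and minor programming. The downside is that a few true Baseline users with poor records may be classed as failures.

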If a subject has less than 4 days of diary data, the total CDAI score will not be calculated and will be considered missing.

Same rule will be applied to average daily stool frequency and average daily abdominal pain.

Bristol Stool Chart

Up to 14 days of diary entries will be evaluated from the ePRO tool for the Bristol Stool Chart calculation. These assessments on the day of endoscopy procedure, the day before endoscopy procedure (due to preparation medications), and 2 days after endoscopy procedure are excluded. The 7 most recent non-missing assessments will be used for the

analysis. The Bristol Stool Chart is calculated as the number of days the subjects with Type 6 or Type 7 divided by the total number days with non-missing assessments, rounded to two decimal.

If a subject has less than 4 days of diary data, the Bristol Stool Chart will not be calculated and will be considered missing.

If a subject achieved reduction from Baseline $\geq 50\%$, this subject will be classified as Responder.

SES-CD Scoring

All colonoscopies shall be performed and recorded in video format. To be eligible for the study, the screening colonoscopy may be performed during the Screening Period (or up to 45 days before the Baseline visit if Amendment 2 is in place at the site). Colonoscopies will also be performed at the Week 12 or 16 visit. Investigators shall provide their SES-CD score assessment on the SES-CD score sheet for the baseline and Week 12 or 16 visits. The investigator SES-CD scores are to be entered in the appropriate eCRF, however neither the Investigator's Baseline nor Week 12 or 16 SES-CD scores will be used for the study's efficacy analyses.

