- Proportion of subjects with decrease in CDAI ≥ 100 points from Induction Baseline over time in Induction Period.
- Proportion of subjects who are IBDQ responders (increase in IBDQ score ≥ 16 points from Induction Baseline) over time in Induction Period.
- Proportion of subjects with IBDQ score ≥ 170 over time in Induction Period.
- Proportion of subjects who achieve steroid-free CDAI < 150 over time in Induction Period among subjects taking corticosteroids at Baseline.
- Proportion of subjects who achieve steroid-free clinical remission over time in Induction Period among subjects taking corticosteroids at Baseline.

- Change from Induction Baseline in fecal calprotectin level over time in Induction Period.
- Change from Induction Baseline in hs-CRP over time in Induction Period.
- SES-CD endpoints without any missing individual variables.
- The proportion of subjects with no anal fissures at Week 16 among subjects with anal fissures at Baseline.
- The proportion of subjects with no draining fistulas at Week 16 among subjects with draining fistula at Baseline.
- The proportion of subjects with no non-draining fistulas at Week 16 among subjects with non-draining fistula at Baseline.
- The proportion of subjects with no any fistulas at Week 16 among subjects with any fistula at Baseline.
- Change from Induction Baseline in Bristol Stool Chart at Week 4 and Week 16.
- The proportion of subjects who achieve Bristol Stool Chart response at Week 4 and Week 16.
- Cross tabulation of Baseline and Week 16 in EIM.
- The proportion of subjects who achieve modified clinical remission at over time in Induction Period among subjects with an average daily SF ≥ 4.0 or average daily AP ≥ 2.0 at Baseline.
- Change from Induction Baseline in EQ-5D over time in Induction Period.
- Change from Induction Baseline in WPAI over time in Induction Period.

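### Bristol Stool Chart response is defined on a score already rounded to two decimals, so two exact 50% reductions (4/7 to 2/7 and 2/6 to 1/6 days) are scored as non-response

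*SAP*

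**What the plan says.** The Bristol Stool Chart rule is in section 6.0 (Analysis Conventions) of the Induction SAP. It has four parts.

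- **Score.** The count of days with "Type 6 or Type 7 divided by the total number days with non-missing assessments", with the result rounded to two decimals.
- **Largest denominator.** Seven days: "The 7 most recent non-missing assessments will be used for the" analysis, drawn from up to 14 diary days after days around an endoscopy are removed.
- **Smallest denominator.** Four days: "If a subject has less than 4 days of diary data, the Bristol Stool Chart will not be calculated".
- **Response.** The sentence opens "If a subject achieved reduction from Baseline", sets an inclusive threshold of 50%, and ends "this subject will be classified as Responder".

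Section 10.3 uses the classification once, among the additional endpoints: "The proportion of subjects who achieve Bristol Stool Chart response at Week 4 and Week 16". The same list also has the change in the Bristol score at those visits.

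Section 6.0 of the Extension SAP repeats the score and responder rule. Its endpoint list in section 10.2 contains no Bristol response.

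**The concern.** A score built on at most seven days takes few values, and many plausible changes are exact halvings that fall on the inclusive 50% threshold. If the score is rounded before the percentage is taken, a small rounding error can move such a subject across the line. Two subjects with the same true reduction could then be classified differently for no clinical reason.

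At stake are the Week 4 and Week 16 Bristol response rates in each arm. They would be slightly too low, by an amount that depends on how often the affected patterns occur.

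**Working it through.** **Inputs.** From Induction SAP 6.0: score = Type 6/7 days ÷ assessed days, rounded to two decimals; 4 to 7 assessed days; response if (Baseline − visit) ÷ Baseline ≥ 0.50. I read this as a relative reduction, the natural reading. The documents give no figure for this endpoint to reproduce.

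**Step 1: the 4-to-2 case on seven days.**
- Unrounded: (4/7 − 2/7) ÷ (4/7) = 0.5000, so response.
- Rounded: 4/7 = 0.5714 → 0.57 and 2/7 = 0.2857 → 0.29. Then (0.57 − 0.29) ÷ 0.57 = 0.4912, so non-response.

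Baseline rounds down and follow-up rounds up, and both shrink the apparent reduction.

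**Step 2: all patterns.** I compared every pair of day counts with denominators 4 to 7 at each visit, including unequal denominators, exact against rounded. Two pairs change class. With equal denominators of 6 or 7, the exact halvings are:

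| Baseline → visit | Rounded scores | Reduction from rounded scores | Class as written |
|---|---|---|---|
| 4/7 → 2/7 | 0.57 → 0.29 | 49.1% | Non-responder (wrong) |
| 2/6 → 1/6 | 0.33 → 0.17 | 48.5% | Non-responder (wrong) |
| 2/7 → 1/7 | 0.29 → 0.14 | 51.7% | Responder |
| 6/7 → 3/7 | 0.86 → 0.43 | 50.0% | Responder |
| 4/6 → 2/6 | 0.67 → 0.33 | 50.7% | Responder |
| 6/6 → 3/6 | 1.00 → 0.50 | 50.0% | Responder |

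Halvings on 4 or 5 days, and those across unequal denominators, also stay responders. No pair with a true reduction below 50% becomes a responder. No fraction with these denominators ties at the second decimal, so the rounding convention does not matter.

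**Step 3: how often 4/7 → 2/7 could occur.** The documents give no Bristol distribution, so all of this is assumption. Take seven days at both visits, with the Baseline and follow-up counts independent of each other.

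*Independent days with one daily chance per visit.* Loss = P(Bin(7, pB) = 4) × P(Bin(7, pF) = 2).
- pB = 0.6, pF = 0.3: (35 × 0.6⁴ × 0.4³) × (21 × 0.3² × 0.7⁵) = 0.290 × 0.318 = 9.2 points.
- pB = 0.8, pF = 0.5: 0.115 × 0.164 = 1.9 points.
- pB = 0.9, pF from 0.2 to 0.5: 0.0230 × (0.164 to 0.318) = 0.4 to 0.7 points.
- pB = 0.95, same pF: 0.00356 × (0.164 to 0.318) = about 0.1 points.

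*Days correlated within subject.* Beta-binomial counts with intra-subject correlation 0.3 to 0.5, Baseline mean 0.6 to 0.8 and follow-up mean 0.2 to 0.5 give about 0.4 points (0.056 × 0.074) to 2.0 points (0.134 × 0.148).

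For the 35 subjects per group planned in section 4.3, 9.2 points is 0.092 × 35 = 3.2 subjects, 2 points is 0.7 and 0.1 points is 0.04.

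**The case against.** **The order of operations is inferred.** The response sentence does not say that the percentage is taken from the rounded score, and a programmer might use day counts. That is true. But the rounded score is the only Bristol value the SAP defines, and nothing points back to unrounded fractions. Following the text gives the misclassification; avoiding it means departing from the text. What stands is that the documents do not show how response was actually programmed.

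**The effect may be very small.** This largely stands. Entry requires average daily stool frequency of at least 2.5 or abdominal pain of at least 2.0, so many subjects may have loose stools almost every Baseline day. Stool form is also likely to be correlated from day to day. Either feature makes a count of exactly 4 of 7 uncommon. A reader could note that with 4 of 7 at Baseline and a 30% daily chance at follow-up, 0.318 ÷ 0.647 = 49% of true responders are lost. That figure applies to one Baseline count under one assumed model and does not measure the effect on the endpoint.

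**Subjects with no loose-stool day at Baseline.** A reader might infer that they stay in the denominator and dilute the rate. The SAP does not say so. Reduction from zero is undefined and the SAP does not address it; counting them as failures follows only if the value is treated as missing and non-responder imputation is applied. Whether to exclude them is a choice of population, separate from the rounding error.

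**The Extension SAP.** Its repeated wording might suggest that extension results are affected too. No Bristol response endpoint is listed there, so at present nothing follows from it.

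**Conclusion.** The point holds as a minor defect in a stated rule. Rounding before the percentage is taken turns two exact 50% reductions, 4/7 to 2/7 and 2/6 to 1/6, into non-response while other exact halvings pass, and the error never adds a responder. This needs only the literal reading of section 6.0 and a relative reduction.

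The size cannot be fixed from the documents. For 4/7 to 2/7 it is about 0.1 to 0.7 points if Baseline loose-stool days are near-universal (daily chance 0.9 to 0.95), about 0.4 to 2 points if days are correlated within subject, and up to about 9 points with independent mid-range days. The 2/6 to 1/6 pattern needs exactly six assessed days at both visits and is not in these figures.

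The reach is one additional endpoint at two induction visits. The co-primary endpoints, the MCPMod dose-response analysis and the listed secondary endpoints do not use it. A reader might infer a material bias in the trial's efficacy conclusions; the documents do not support that.

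**What to change.** In section 6.0 of the Induction SAP, state that the percent reduction for Bristol response is computed from unrounded day fractions (or the day counts themselves), with two-decimal rounding for display only. Then 4/7 to 2/7 and 2/6 to 1/6 both give exactly 50% and count as response. Use the same wording in section 6.0 of the Extension SAP in case a Bristol response is ever analysed there.

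The cost is one sentence per document and no new data. Section 3.0 of the Extension SAP says that the Induction SAP was signed off before the December 2016 induction lock. For induction, the practical step is therefore to check how response was derived and, if rounded scores were used, to rerun that one endpoint at Week 4 and Week 16.
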